To control for Type I error, the critical *p* values for each assessment will be determined with the unweighted Bonferroni method,⁵⁸ dividing the critical value of *p* < .05 by the number of comparisons conducted for a given assessment. As discussed in Shaffer,⁵⁸ corrections for familywise error involve correcting alphas separately for each family of hypotheses. Although defining families is a rather straightforward process in a simple experiment (e.g., 1 family in a study with a single dependent variable and 1 independent variable with several levels), Shaffer argues that defining families becomes more complicated (and potentially more problematic) in large, more complex studies where alpha corrections can substantially lower statistical power (i.e., increase Type II error). To balance concerns about Type I and Type II error, a family will therefore be defined as the set of measures derived from a particular outcome assessment, and an alpha correction procedure will then be used (the unweighted Bonferroni) to control for error-rates within families. The resulting critical *p* values will be: FPI, 0.05/16 = 0.003; CFSQ, 0.05/3 = 0.017; FKQ, 0.05/6 = 0.008; compensation trials, 0.05/1 = 0.05; EAH, 0.05/1 = 0.05; FPQ, 0.05/2 = 0.025; CEBQ, 0.05/8 = 0.006; BMI, 0.05/2 = 0.025. Only results that meet these critical values will be reported in the primary analyses. To minimize the probability of Type II error, these critical values will be applied only to *p* values for the simple main effects analyses of time given the limited power of condition by time interactions in this type of design.⁵⁹

Finally, exploratory analyses will be run on variables that show condition by time interactions in the pre-post analyses reported by [name] and colleagues⁴⁵ but do not show significant interactions in the current study. Because the smaller samples at follow-up may reduce the power to find significant time by condition interactions at 6- and 12-months, simple main effects analyses of time were be run separately for the control and prevention groups to determine if the condition effects found in earlier pre-post analyses¹⁶ persisted for the variables in the current study.

REFERENCES

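### Holm's step-down would replace the single-step Bonferroni within each multi-measure family at no cost in error control, for a modest gain in power

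*Combined protocol and SAP*

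**What the plan says.** The section DATA ANALYSES of the combined protocol and SAP sets the critical values by "dividing the critical value of *p* < .05 by the number of comparisons conducted for a given assessment". On families it states that "a family will therefore be defined as the set of measures derived from a particular outcome assessment", and that "an alpha correction procedure will then be used (the unweighted Bonferroni) to control for error-rates within families". The resulting cut-offs are "FPI, 0.05/16 = 0.003; CFSQ, 0.05/3 = 0.017; FKQ, 0.05/6 = 0.008" and "compensation trials, 0.05/1 = 0.05; EAH, 0.05/1 = 0.05; FPQ, 0.05/2 = 0.025; CEBQ, 0.05/8 = 0.006; BMI, 0.05/2 = 0.025". They are fixed: "Only results that meet these critical values will be reported in the primary analyses".

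The same paragraph shows concern for power. It defends small families on the ground that "alpha corrections can substantially lower statistical power". It then limits the critical values to the simple main effects of time, again citing Type II error. Earlier in the section, simple main effects are described as the follow-up to a significant condition by time interaction, and 95% confidence intervals are planned with no multiplicity adjustment mentioned. No stepwise procedure appears, and no reason is given for the single-step form.

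**The concern.** A single-step rule holds every measure to 0.05/k even after other measures in the family have been rejected. Holm relaxes the threshold after each rejection and pays nothing for it in family-wise error. The plan already makes two concessions to save power, narrow families and correction of the follow-up tests only, and both loosen Type I control. Holm would recover some power without loosening it. At stake is how many of the changed measures within a family are identified. Whether any measure in the family is identified is essentially unaffected.

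**Working it through.** **1. The plan's figures.** With α = 0.05 and k = 16, 3, 6, 1, 1, 2, 8 and 2, α/k is 0.003125, 0.016667, 0.008333, 0.05, 0.05, 0.025, 0.00625 and 0.025. All eight stated values reproduce to three decimals. CFSQ is rounded up: 3 × 0.017 = 0.051.

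**2. Holm's thresholds.** The i-th smallest p is compared with 0.05/(k − i + 1), stopping at the first failure:
- FPI: 0.00313, 0.00333, 0.00357, ..., 0.025, 0.05
- CEBQ: 0.00625, 0.00714, ..., 0.05
- FKQ: 0.00833, 0.01, 0.0125, 0.0167, 0.025, 0.05
- CFSQ: 0.0167, 0.025, 0.05
- FPQ and BMI: 0.025, 0.05
- Compensation trials and EAH (k = 1): 0.05, unchanged

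**3. Same guarantee, never fewer rejections.** Each threshold is at least 0.05/k, so every p at or below 0.05/k is rejected by both methods. If m₀ of the k nulls are true, the first true null to be rejected faces a threshold of at most 0.05/m₀. The chance that any of the m₀ falls below that is at most m₀ × 0.05/m₀ = 0.05, whatever the dependence.

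**4. Power with the interaction gate ignored.** Assumptions, since the documents give no sample size, effect size or standard deviation: two-sided normal tests, correlation 0.3 between measures, 80% unadjusted power per true effect. The non-centrality is then 1.96 + 0.84 = 2.80, and Bonferroni power is Φ(2.80 − z), with z the normal quantile at 1 − 0.025/k. For k = 2, Φ(2.80 − 2.24) = 71%. For k = 16, Φ(2.80 − 2.955) = 44%. Holm power is by simulation. With every measure in the family truly affected:

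| Family | k | Bonferroni | Holm | Gain (points) |
|---|---|---|---|---|
| FPQ, BMI | 2 | 71.2% | 76.9% | 5.7 |
| CFSQ | 3 | 65.9% | 74.2% | 8.3 |
| FKQ | 6 | 56.6% | 67.6% | 11.0 |
| CEBQ | 8 | 52.7% | 64.0% | 11.3 |
| FPI | 16 | 43.9% | 54.3% | 10.4 |

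With half the measures affected, the gain is about 3 points (FPI, 8 of 16: 43.9% to 46.9%). FPI with 4 of 16 gains 1.2 and with 2 of 16 gains 0.4. With one real effect, families gain 0 to 0.3. Simulated family-wise error stayed below 0.05 for both methods at this correlation. The chance of at least one true detection is essentially unchanged, because Holm's first step is the Bonferroni cut-off.

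**5. Power with the gate.** The corrected tests follow a significant, uncorrected interaction. Let the gate be independent of the follow-up test, and set p = 1 where it is not passed. Bonferroni power is then gate power times the figure above. For FPQ at a 50% gate, 0.50 × 71.2% = 35.6%. With all effects real and gates independent across measures, Holm adds about 0.5 points at a 30% gate, 1.5 to 2 at 50%, and 3.5 to 6 at 80%. If the interaction statistics are also correlated at 0.3, the 50% gate gives FPQ 35.8% to 37.6%, CFSQ 33.0% to 35.3%, FKQ 28.3% to 31.0% and FPI 22.0% to 24.3%, which is about 2 to 3 points. With few real effects the gated gain is near zero.

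**The case against.** The case for leaving the plan alone is that unweighted Bonferroni is valid, prespecified and fully tabulated, and that the plan aims to balance the two error types, not to maximise power. That stands, and it makes this an efficiency point. It does not supply a reason for the single-step form. The usual reason, matching simultaneous confidence intervals, is absent because only ordinary 95% intervals are planned.

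A reader might infer that the 6 to 11 points in the table are what the trial would gain. The documents do not support that. The corrected tests sit behind an interaction test whose power the plan itself calls limited. If that gate is weak, it loses far more power than Bonferroni does, and Holm returns only a point or two.

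A reader might also infer that real programme effects would be missed because of Bonferroni. The documents do not support that either. The critical values apply to simple effects of time, while the condition by time tests carry no correction and would be unchanged.

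It is also fair to object that swapping the method's name is not enough. Holm must rank a defined set of k p values. A measure may give several (simple effects of time in two arms, pairs of time points) or none (gate not passed). The objection is right about the wording of the fix, but it is no argument for Bonferroni, which needs the same definition. With two independent p values per measure (an assumption), family-wise error at 0.05/k would be 1 − (1 − 0.05/k)^(2k): 9.5% for k = 16 and 9.75% for k = 1.

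Lastly, the statement that Holm never rejects less is exact only against 0.05/k. A CFSQ p of 0.0168 passes the plan's rounded 0.017 but fails Holm's first step of 0.01667.

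**Conclusion.** The point holds as a free improvement and not as an error in the plan: nothing here biases a result or inflates error. In the six families with more than one measure (FPI, CFSQ, FKQ, FPQ, CEBQ, BMI), single-step Bonferroni is uniformly dominated by Holm at the same family-wise error of 0.05. That part rests on no distributional assumption. It needs only one valid p value per measure.

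The size does rest on assumptions (correlation 0.3, 80% unadjusted power, and a gate independent of the follow-up). It is modest: at most about 6 to 11 points, probably less once the gate is counted, and negligible if only one or two measures in a family respond. Compensation trials and EAH gain nothing.

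**What to change.** In DATA ANALYSES, replace the unweighted Bonferroni by Holm's step-down within FPI, CFSQ, FKQ, FPQ, CEBQ and BMI. Further:
- Use the unrounded thresholds 0.05/k, 0.05/(k − 1), ..., 0.05, or report Holm-adjusted p values against 0.05.
- State which single p value per measure, from the simple main effects of time, enters the ranking. For BMI, name the two measures: weight category is analysed by a multinomial regression that tests the main effect of condition and yields no simple effect of time.
- Keep k at the full family size and set p = 1 for a measure whose interaction is not significant. This can only raise a p value, so the guarantee survives. Shrinking k to the measures that pass the gate could break it.
- Settle k for CEBQ, where the divisor is 8 but the measures section targets three subscales.

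The cost is a few sentences of SAP text and a small change in code, with no extra data and no loss of error control. The plan refers to pre-post analyses already reported, so the change should be dated, declared as an amendment, and made before the follow-up results are tested.

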Data collections for both the prevention and control arms will be conducted in small group settings led by trained staff members of Hispanic descent who are proficient in reading, speaking, and writing in English and Spanish. Data collectors will be blinded to participant group allocation. For parents with low literacy skills, data collectors will read the questions to the parents and recorded their responses. Child assessments will be completed at the same time as the parents in a separate room. Most measures are validated for use with preschoolers and Hispanic samples.

Parent Feeding Measures (Practices, Styles, and Knowledge)

Food Parenting Inventory (FPI). The FPI is a parent-report measure of feeding *practices* with 16 subscales assessing 3 higher level feeding constructs: 1) Encourage Trying New Foods (offer new foods, encourage exploration of new foods, urge child to eat new foods, and repeated presentation of new foods), 2) Mealtime Structure (family meals, regular timing of meals and snacks, inconsistent mealtimes, indifferent feeding, child involvement in food preparation, parent decides portion sizes, and serving measured portions) and 3) External Control (pressure to eat, restriction, food as reward, responsiveness to child's fullness cues, and monitoring).⁴¹

Caregiver's Feeding Styles Questionnaire (CFSQ). The CFSQ is a parent-report questionnaire developed to measure feeding *styles* in parents with low incomes.⁴² The questionnaire was developed for use with parents of children ages 3 to 11. Parents indicate how often they use 7 child-centered (e.g., reasoning, complimenting) and 12 parent-centered (e.g., demands, threats) feeding directives. Two feeding style dimension scores of demandingness and responsiveness are derived from the child-centered and parent-centered items. Parents are classified into 4 feeding style categories of authoritarian, authoritative, indulgent, and uninvolved. Evidence of test-retest reliability, internal consistency, convergent and predictive validity has been demonstrated in Hispanic samples and samples with low incomes.⁴²⁻⁴⁴

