Eating in the Absence of Hunger (EAH). Child *eating self-regulation* will also be measured by the EAH task developed by Fisher and Birch.⁴⁹ On the day the child receives the high energy preload drink as part of the compensation task and approximately 10-15 minutes after finishing the standard meal, the child will be presented with sweet and savory snacks along with age appropriate toys. Children will be left with the food and toys for 10 minutes and will be told they can eat what they want, sit quietly, and/or play with the toys. This task will be administered in the centers to several children at once, although children will complete the task individually through the use of portable screens creating a separate assessment area for each child. Remaining snacks will be measured and total kcal consumed will be calculated. Scores will reflect the total number of kcal eaten in the absence of hunger. This assessment has been used predominately with White children and has been validated with preschoolers; a few studies have used the EAH task with Hispanic children.⁵⁰

Child Eating Behavior Questionnaire (CEBQ). The CEBQ is a parent-report measure assessing 8 dimensions of child eating behaviors.⁵¹ Validity and reliability have been demonstrated.⁵¹ For this study, only the subscales of food responsiveness, emotional overeating, and satiety responsiveness are targeted because they are considered parent-report measures of child eating behaviors related to eating self-regulation. The CEBQ has shown adequate validity and reliability⁵¹ and has been used successfully with Hispanic parents of preschoolers with low-income levels.⁵²

Child Tasting Panel Observation. A standardized food tasting protocol, developed by Sullivan and Birch⁵³ and modified by Moding, Bellows, Grimm, & Johnson,⁵⁴ will be administered to measure taste preferences (Yummy, Just OK, or Yucky) and children's willingness to try new foods (1 = tried; 0 = refused). Each child will be asked to try bite-sized samples of 9 familiar and novel foods from a variety of food groups including broccoli, beets, couscous, garbanzo beans, gouda cheese, grapefruit, kale, okra, and papaya. Each food will be served in a small two-ounce cup and include 3 small pieces of the food. This assessment tool was developed for a large, 3-year longitudinal study of preschoolers in Colorado (41% Hispanic).⁵⁴

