Food Preferences Questionnaire (FPQ). The variety of fruit and vegetables consumed by the children will be measured by a food preference questionnaire adapted from Skinner and colleagues.²⁹ Parents will report on their child's food consumption from 112 food and drink items using 3 categories: never tried it, tried – liked it, or tried – did not like it. Similar measures have been used successfully by the Food and Drug Administration in the Total Diet Study.²⁹ Only data on the fruit and vegetables will be analyzed given the program emphasis on trying fruit and vegetables, and the fact that the vast majority of foods in the questionnaire are fruit and vegetables. Two measures will be examined: the total number of vegetables tried out of 50 and the total number of fruits tried out of 27. This questionnaire has been used predominately with White samples.²⁹

Anthropometrics. Trained staff, following standardized procedures, will measure parent and child heights (to the nearest 0.1 cm) and weights (to the nearest 0.1 kg).⁵⁵ Two height and weight measures will be averaged for each parent and child. Age- and gender-specific BMI z-scores for each child will be calculated. Children will be classified into healthy weight (5th to < 85th percentile), overweight (\geq 85th to < 95th percentile), and obese (\geq 95th percentile) according to Centers for Disease Control and Prevention standards.⁵⁶ BMI scores will be calculated for the parent and classified as low and normal weight (BMI < 24.9), overweight (BMI \geq 25 to < 30) or obese (BMI \geq 30).

DATA ANALYSES

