All analyses will be intention-to-treat analyses—that is, data from parents and children will be analyzed based upon the condition to which they will be initially assigned, regardless of the number of classes they attended. This approach, although it reduces power, maintains the internal validity of the RCT design.⁵⁷ Because participants will be nested within classes, the intraclass correlations (ICC's) will be first examined for each dependent variable to determine if a statistical approach controlling for such nesting will be necessary. All outcome variables (except for child weight status) will be examined using multilevel analyses with the SPSS (version 25) Mixed Models Program. The SPSS Mixed Model program does not provide measures of effect sizes; however, 95% confidence intervals will be included for precision. Child sex, child age in months, and child BMIz at pre-test will be control variables in all of the multilevel analyses. Significant condition by time interactions will be followed up with simple main effects analyses and multi-level analyses comparing pairs of time points. The main analyses will be conducted on participants who have data at all 4 time points. Paired comparisons will use all available data. Most of the missing data will be addressed by calculating the subscale scores using the mean of the non-missing items in that particular subscale. If greater than 25% of a subscale's items are blank, then the score will be considered missing. The multilevel models also will be rerun examining (1 at a time) possible program moderators: child age, child sex, child BMI status, and location (Houston versus Pasco). Moderation will be tested by examining the significance of the moderator by condition by time interactions.

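### The CEBQ significance threshold divides 0.05 by eight subscales, but the Measures section targets only three

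*Combined protocol and SAP*

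**What the plan says.** In the Data Analyses section, Type I error is controlled by an unweighted Bonferroni correction within each assessment: 0.05 is divided "by the number of comparisons conducted for a given assessment". Eight critical values are listed, among them "CEBQ, 0.05/8 = 0.006". Results that miss these values are left out of the primary report. The values are applied only to p values from "simple main effects analyses of time given the limited power of condition by time interactions in this type of design".

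The CEBQ entry under Measures first describes the whole instrument: "The CEBQ is a parent-report measure assessing 8 dimensions of child eating behaviors". It then narrows it for this trial: "only the subscales of food responsiveness, emotional overeating, and satiety responsiveness are targeted". The reason given is that these three are parent-reported indicators of eating self-regulation.

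**The concern.** A Bonferroni divisor should equal the number of tests in the family, and the plan's own rule says so. For the CEBQ the divisor equals the size of the published instrument, while the Measures section selects three of its eight dimensions. Both statements cannot describe the same analysis.

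The threshold also decides what is reported. A CEBQ finding that falls between the two candidate values would be in the primary report under one reading and out of it under the other. The three named subscales are parent-report measures of eating self-regulation, the construct in the trial's title and objective. An oversized divisor also works against the plan's stated aim of balancing Type I and Type II error.

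**Working it through.** **Inputs**

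- Family-level alpha: 0.05 (Data Analyses).
- Rule: critical p = 0.05 / k, where k is the number of comparisons for the assessment (Data Analyses).
- Printed CEBQ divisor: k = 8 (Data Analyses).
- CEBQ dimensions in the instrument: 8; subscales targeted in this study: 3 (Measures, CEBQ).

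**Reproducing the printed figure**

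0.05 / 8 = 0.00625, which rounds to the printed 0.006. The other seven listed values also follow from their own divisors, so the arithmetic is not at issue.

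**Applying the rule to the three targeted subscales**

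- 0.05 / 3 = 0.01667, or 0.017 at the plan's rounding.
- Ratio of the two thresholds: 0.01667 / 0.00625 = 8 / 3 = 2.67.
- Subscales counted in the divisor but not targeted: 8 − 3 = 5.

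**Does the plan count analysed measures elsewhere?**

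| Assessment | Instrument, as described in Measures | Measures analysed | Divisor |
|---|---|---|---|
| Food Preferences Questionnaire (FPQ) | 112 items | 2 | 2 |
| Food Parenting Inventory (FPI) | 16 subscales | 4 + 7 + 5 = 16 | 16 |
| CEBQ | 8 dimensions | 3 targeted | 8 |

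The FPQ is the informative comparator. Its analysis is restricted to part of the instrument ("Two measures will be examined: the total number of vegetables tried out of 50 and the total number of fruits tried out of 27") and its divisor follows the restriction. The FPI, a measure "with 16 subscales assessing 3 higher level feeding constructs", is consistent with counting analysed measures, but there the whole instrument and the analysed set coincide, so it cannot separate the two conventions. The divisors for the feeding styles questionnaire, the feeding knowledge questionnaire and BMI were not examined for this point.

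**What each mismatch would do (nominal Bonferroni sum, one test per subscale)**

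- Three subscales tested at 0.00625: 3 × 0.00625 = 0.01875 of the 0.05 allowed, so the threshold is conservative.
- Eight subscales tested at 0.01667: 8 × 0.01667 = 0.133, which exceeds 0.05.

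The second line shows why the count must be settled before the threshold is changed. These sums are not achieved familywise error rates, because simple main effects are also run by arm and time points are compared in pairs.

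**Where it bites**

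In the main analyses, "Significant condition by time interactions will be followed up with simple main effects analyses". The critical values apply at that follow-up step and not to the interaction test itself. The affected results are therefore CEBQ simple main effects of time with p between 0.006 and 0.017.

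**The case against.** The best defence of 8 is the plan's definition of a family as all the measures that come from one assessment. The CEBQ has eight dimensions, so on that definition a divisor of eight is a possible reading. *Targeted* also need not mean *tested*: for the FPQ the plan says outright which data will be analysed, and for the CEBQ it uses the softer word. A critic would add that the convention of counting analysed measures rests on one informative comparator, and that a conservative threshold does little harm.

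Parts of this stand. The documents do not show which count was intended, the evidence from other assessments is essentially the FPQ alone, and the consequence is limited. The conflict remains, however. A divisor of eight matches the stated rule only if all eight subscales are compared, and then the Measures section is wrong to say *only* three. If *targeted* means no more than emphasised, the plan does not state how many CEBQ outcomes it has. On either reading one of the two sections needs correcting. Being conservative does not settle it either, because the threshold controls what enters the primary report.

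**Conclusion.** The concern holds: the CEBQ threshold and the CEBQ description in Measures are inconsistent as written. If three subscales are tested, the printed 0.006 is about 2.7 times stricter than the plan's rule gives (0.00625 against 0.0167). It then adds no false positives but removes CEBQ simple main effects of time with p between 0.006 and 0.017 from the primary report. If eight are tested, 0.006 is correct and the Measures text is wrong.

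The condition by time tests are unaffected. No statement about lost power is made, because the documents give neither a total sample size nor an effect size. The conclusion rests on the plan's rule of counting comparisons and on reading *only* in its ordinary sense. The point should be corrected, though it does not threaten the trial's main inference.

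**What to change.** State in the CEBQ entry under Measures how many subscales will be tested, then make the two sections agree:

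- **If three:** change the entry in Data Analyses to 0.05/3 = 0.017.
- **If all eight:** keep 0.05/8 = 0.006 and remove the restriction to three subscales from Measures.

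Add a dated note recording when the divisor was fixed. The reference list cites short-term results of the programme published in March 2020, and the protocol is dated March 2022. The documents do not show whether those results included the CEBQ or when the divisor was chosen. Moving to 0.017 would loosen a threshold after that publication; the note discloses this but does not remove it.

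The cost is one entry or one sentence, plus the note, with no new data and no change to the models. As a separate minor tidy-up in the same list, the Child Tasting Panel has no entry. Naming its analysed measures would fix its divisor under the general rule.

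### The rule that only results meeting the critical values are reported lets null outcomes drop out of the primary results and exaggerates the within-arm changes that remain.

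*Combined protocol and SAP*

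**What the plan says.** All of this stands in the Data Analyses section.

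- Thresholds: an unweighted Bonferroni correction is made within each assessment, "dividing the critical value of *p* < .05 by the number of comparisons conducted for a given assessment". The values are "FPI, 0.05/16 = 0.003; CFSQ, 0.05/3 = 0.017; FKQ, 0.05/6 = 0.008; compensation trials, 0.05/1 = 0.05; EAH, 0.05/1 = 0.05"; "FPQ, 0.05/2 = 0.025; CEBQ, 0.05/8 = 0.006; BMI, 0.05/2 = 0.025".
- Reporting rule: "Only results that meet these critical values will be reported in the primary analyses".
- Scope of the thresholds: "these critical values will be applied only to *p* values for the simple main effects analyses of time". The reason given is the limited power of the interaction test.
- Order of testing: simple main effects and pairwise time comparisons follow only a significant condition by time interaction.
- Precision: the multilevel analyses give no effect sizes, but "95% confidence intervals will be included for precision".
- Second route: exploratory simple effects of time, run separately in each arm, are planned for variables that showed an interaction in the earlier pre-post analyses but show none here.
- Child BMI category is handled apart, by a multinomial logistic regression on the main effect of condition.

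**The concern.** A critical value should decide what is called significant. Here it also decides what is reported. That has two consequences.

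First, the reader may not see the outcomes on which the program made no detectable difference. The stated objective is to test efficacy across many feeding and eating measures, and a list of the passing results alone does not show how many were tried and failed.

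Second, an estimate kept because it crossed a threshold is on average too large. The stricter the threshold and the lower the power, the larger the exaggeration. The thresholds here go down to 0.003, and the plan itself concedes limited power for the interaction.

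Moving the thresholds to a different test would not remove the problem, because any significance filter on reporting has the same effect.

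**Working it through.** **1. The plan's own figures.** 0.05/16 = 0.003125, 0.05/3 = 0.016667, 0.05/6 = 0.008333, 0.05/1 = 0.05 (twice), 0.05/2 = 0.025 (twice) and 0.05/8 = 0.00625. All eight stated values reproduce to three decimals. The divisors sum to 16 + 3 + 6 + 1 + 1 + 2 + 8 + 2 = 39 comparisons. The CEBQ divisor is 8, although the Measures section targets only three CEBQ subscales; with three, the total would be 34.

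**2. What can appear in the primary results.**

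| Situation | What the plan says |
|---|---|
| Interaction significant, simple effect of time passes | Reported |
| Interaction significant, simple effect of time fails | Not reported in the primary analyses |
| Interaction not significant, variable showed an interaction in the earlier pre-post analyses | Exploratory analysis |
| Interaction not significant, no earlier interaction | Nothing stated |
| Tasting panel | No critical value listed |
| BMI category (multinomial model) | A BMI threshold is listed, but the thresholds apply only to simple effects of time, which this model does not contain |

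No sentence in the document commits the plan to showing every outcome.

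**3. Size of the exaggeration.** The filtered quantity is change within an arm. For two time points, in units of the outcome SD, the standard error is SE = sqrt(2(1 − ρ)/n), where ρ is the correlation between time points. Let μ = d/SE, and let c be the two-sided normal critical value. Ignoring the far tail, which is negligible here:

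- chance of passing = Φ(μ − c)
- mean reported change / true change = 1 + φ(c − μ) / [μ Φ(μ − c)]

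The documents give only 8 to 10 families per condition per wave, with no number of waves. So n = 75 and 100 per arm, d = 0.3 SD, ρ = 0.5 and 0.7, and two-sided testing are all assumptions.

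Worked case: n = 75, ρ = 0.5, threshold 0.003. SE = sqrt(1/75) = 0.1155, μ = 0.3/0.1155 = 2.598 and c = 2.968. Then φ(0.370) = 0.3726 and Φ(−0.370) = 0.3558. The ratio is 1 + 0.3726/(2.598 × 0.3558) = 1.40.

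| ρ | n per arm | Passes at 0.003 | Overstated by | Passes at 0.05 | Overstated by |
|---|---|---|---|---|---|
| 0.5 | 75 | 36% | 40% | 74% | 17% |
| 0.5 | 100 | 51% | 26% | 85% | 9% |
| 0.7 | 75 | 65% | 17% | 92% | 5% |
| 0.7 | 100 | 82% | 8% | 97% | 2% |

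The result depends strongly on d. With ρ = 0.5 and the 0.003 threshold, the same formula gives 75-99% for d = 0.2 and 1-4% for d = 0.5.

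**4. The same check without a sample size.** Fix the power at p < 0.05 instead. The ratio of reported to true effect at thresholds 0.05 and 0.003 is 1.06 and 1.20 for 90% power, 1.12 and 1.32 for 80%, and 1.41 and 1.78 for 50%.

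**5. Limits of the model.** It treats one pairwise change. A simple effect of time over four time points may be an omnibus test, which this formula does not describe. It also leaves out the prior selection on a significant interaction.

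**The case against.** The sentence could be shorthand for reporting results as significant. That is possible, but the text does not say it, and if it is the intention, the replacement wording below costs nothing.

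All outcomes are still analysed, so the defect lies in reporting and can be corrected at write-up without new data. This stands, and it is a reason why the change is easy.

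Three stronger readings are tempting, and the documents do not support them.

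- A reader might infer that no outcome can appear unless its p value passes a critical value. The critical values do not apply to the condition by time interaction, which is the between-arm test. The plan is silent on how non-significant interactions are reported; it does not say that they will be withheld. The exploratory analyses can also bring some null outcomes into view, although that set is itself chosen on earlier significance.
- A reader might infer that confidence intervals will exist only for the passing results. The promise of intervals carries no significance condition. What is missing is a commitment to show them for every outcome.
- A reader might size the bias with the between-arm standard error sqrt(2/n). With the same n and 0.3 SD, that gives an overstatement of 66-89% at 0.003 and 33-48% at 0.05. It describes a different statistic: the plan filters within-arm change, whose standard error is smaller than this whenever ρ is positive.

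**Conclusion.** The concern holds in this form. As written, the plan has a significance filter on its primary report, acting on within-arm changes over time, with no commitment to show the rest. Null outcomes can be missing, and the changes shown are exaggerated on average.

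The direction follows from selecting on p. The size cannot be fixed from the documents. Under the assumptions stated (0.3 SD, 75 to 100 families per arm, ρ of 0.5 to 0.7), it runs from about 8% to 40% at the strictest threshold and from about 2% to 17% at 0.05. It is larger for smaller true changes and close to nil for large ones.

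The documents do not support saying that all null results will be hidden, or that the between-arm estimates are inflated by any particular amount.

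**What to change.** Replace the reporting sentence with:

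> All prespecified outcomes will be reported whatever their p value, with the condition by time estimate (between-arm difference in change), 95% CI and p value at each follow-up, and for BMI category the condition odds ratios with 95% CI from the multinomial model. The critical values decide only which results are called statistically significant.

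This removes the selection, so the expected ratio of reported to true effect returns to 1. It also makes the randomized comparison, not the within-arm change, the quantity that is always shown. It needs no new data and leaves the critical values as they are. The cost is a longer results table or a supplement, including the between-arm contrasts at each follow-up.
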